## Informed Consent/Assent

10. Participant or participant's caregiver(s) (according to local laws) is/are willing and able to give signed informed consent/assent for participation in the study including compliance with the requirements and restrictions listed in the ICF and in [Section 10.2.3](#).
11. Participant's caregiver(s) are willing to allow the responsible authorities to be notified of participation in the study, if mandated by local law.
12. Participant's caregiver completes  $\geq 25$  days of daily Reminder Diary entries during the first 28 days of the baseline period.

## Part B Only:

13. Has completed Part A of this study.
14. Was compliant with all requirements of Part A (eg, dosing, seizure eDiary, visits/procedures), in the clinical judgement of the investigator and/or sponsor.

## 5.2. Exclusion Criteria

Participants are excluded from the study if ANY of the following criteria apply:

### Medical Conditions

15. Has a history of psychogenic non-epileptic seizures that confounds the assessment of the primary efficacy measure.
16. Has clinically significant unstable medical condition(s), other than EMAS.
17. Has a clinically significant illness in the 28 days prior to screening (Part A Visit 1) or randomization (Part A Visit 3), other than epilepsy, which in the opinion of the investigator could affect seizure frequency.
18. Has presence of focal seizures or persistent focal epileptiform discharges on EEG.
19. Has a history of infantile spasms.
20. Has moderate to severe neurocognitive and/or developmental delay prior to seizure onset.
21. Has a progressive neurological condition.
22. Has known or suspected hypersensitivity to cannabinoids or any of the excipients of GWP42003-P such as sesame oil.
23. Is unwilling or unable to remain stable on concurrent ASMs throughout the study.
24. Has, in the opinion of the investigator, clinically significant abnormalities in the ECG measured at screening (Part A Visit 1), or any concurrent cardiovascular conditions, which will interfere with the ability to read their ECGs.
25. Has significantly impaired hepatic function at the screening visit (Part A Visit 1) or prior to dosing, defined as any of the following:
  - ALT or AST  $> 5 \times$  ULN
  - TBL (serum total bilirubin)  $> 1.5 \times$  ULN or INR  $> 1.5$ . Note that for participants diagnosed with Gilbert's disease, TBL  $> 3.0 \times$  ULN and/or direct bilirubin  $> 1 \times$  ULN are exclusionary.
  - Serum ALT or AST  $\geq 3 \times$  ULN with the presence of fatigue, nausea, vomiting, right upper quadrant pain or tenderness, fever, rash, and/or eosinophilia ( $> 5\%$ ).
  - Elevated ALT or AST at screening (Part A Visit 1), should be discussed with the medical monitor prior to randomization (Part A Visit 3); the medical monitor may allow for a confirmatory re-draw prior to randomization.

*This criterion can only be confirmed once the laboratory results are available.*

26. Has clinically significant impaired renal function at screening (Part A Visit 1), as evidenced by an estimated glomerular filtration rate (Schwartz equation)  $< 60$  mL/min.

27. Is a female participant of CBP, who is pregnant (positive pregnancy test), lactating or planning pregnancy during the course of the study and for 3 months thereafter.
28. Participant has any known or suspected history of alcohol or substance use disorder.
29. Any clinically significant abnormalities identified following a physical examination or laboratory assessments of the participant that, in the opinion of the investigator, would jeopardize the safety of the participant if they take part in the study.
30. Participant has any other clinically significant disease or disorder which, in the opinion of the investigator, may either put the participant, other participants, or site staff at risk because of participation in the study, may influence the result of the study, or may affect the participant's ability to take part in the study.

### **Prior Therapy**

31. Is currently treated with Epidiolex/Epidyolex or recently received treatment with Epidiolex/Epidyolex within 28 days prior to screening (Part A Visit 1).
32. Has experienced a lack of efficacy and/or poor tolerability to an adequate treatment regimen of Epidiolex/Epidyolex based on medical history and the clinical judgment of the investigator. Participants who discontinued treatment for reasons other than safety, tolerability, or lack of efficacy and previously received Epidiolex/Epidyolex  $\geq$  28 days prior to screening (Part A Visit 1) may be eligible for the study after consultation with the medical monitor and/or sponsor representative.
33. Has a change in anticonvulsant therapies within 28 days of starting the baseline period (Part A Visit 2), including ASMs or settings on vagal nerve stimulator.
34. Has any planned clinical interventions or intends to change any or all medications that may impact seizures during the study.
35. Has undergone surgery for epilepsy in the 6 months prior to screening (Part A Visit 1).
36. Is being considered for epilepsy surgery or any procedure involving general anesthesia during the study.
37. Has initiated a ketogenic diet within 28 days prior to starting the baseline period (Part A Visit 2). Participants who are stable on a ketogenic diet for  $\geq$  28 days and willing to remain on a stable epilepsy dietary therapy (eg, ketogenic diet, Atkins diet, low glycemic index diet) during the study, are eligible for inclusion.
38. Has initiated felbamate within 12 months prior to screening (Part A Visit 1). Participants who are stable on a felbamate for  $\geq$  12 months are eligible for inclusion.
39. Is currently being treated with or had previously (within 3 months prior to screening [Part A Visit 1]) received intravenous immunoglobulin treatment or plasma exchange for the treatment of seizures.

## Prior/Concurrent Clinical Study Experience

40. Has participated in a clinical study involving administration of an IMP (new chemical entity) or medical device (eg, vagal nerve stimulator) within 28 days prior to screening (Part A Visit 1).
41. Has previously been randomized, completed, or withdrawn from this study.

## Alcohol and Drugs

42. Is currently using a drug of abuse or current nonprescribed use of any prescription drug.
43. Is currently using or has used recreational or medicinal cannabis, cannabinoid-based medications, products, or supplements (botanical or synthetic) within 28 days prior to screening (Part A Visit 1).
44. Mother (if breastfeeding the participant) is currently using or has used recreational or medicinal cannabis, cannabinoid-based medications, products, or supplements (botanical or synthetic) within 28 days of screening (Part A Visit 1).

## Other Exclusions

45. History of suicidal behavior, current suicidal risk as determined from history, or presence of active suicidal ideation as indicated by a positive response to Item 4 or Item 5 on the C-SSRS. The C-SSRS criterion applies only to participants 4 to 18 years of age.
46. Is unwilling or unable to comply with all study requirements, including accurate eDiary completion.
47. Participants who, in the opinion of the investigator (or designee), should not participate in this study.
48. Has travel planned outside their country of residence during the study, unless the participant has confirmation that the IMP is permitted in the destination country and all stops along the way.

## Part B Only:

49. Has significantly impaired hepatic function at Part A Visit 9, defined as any of the following:
  - ALT or AST  $> 5 \times$  ULN
  - TBL (serum total bilirubin)  $> 1.5 \times$  ULN or INR  $> 1.5$ . Note that for participants diagnosed with Gilbert's disease, TBL  $> 3.0 \times$  ULN and/or direct bilirubin  $> 1 \times$  ULN are exclusionary.
  - Serum ALT or AST  $\geq 3 \times$  ULN with the presence of fatigue, nausea, vomiting, right upper quadrant pain or tenderness, fever, rash, and/or eosinophilia ( $> 5\%$ ). The medical monitor may allow for a confirmatory re-draw prior to rollover.

50. Meets any exclusion criteria at Part B Visit 1.

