### **2.3. Benefit/Risk Assessment**

Participants in the current study may experience some improvement of symptoms (beyond that of an assessment of their medical status) from participating in the study. Refer to [Section 2.2](#) for details regarding antiseizure efficacy observed in previous epilepsy clinical studies with GWP42003-P, including patients with EMAS from the EAP. The risks of participation are primarily those associated with adverse reactions to the IMP, although there may also be some discomfort from collection of blood samples and other study procedures. More information about the known and expected benefits, risks, and reasonably anticipated AEs associated with GWP42003-P may be found in the current approved version of the IB (GWP42003-P IB).

GWP42003-P is purified CBD, approved in the US as Epidiolex®, indicated for the treatment of seizures associated with LGS, DS, and TSC in patients 1 year of age and older and approved in the EU, indicated for the adjunctive treatment of seizures associated with LGS and DS, in conjunction with clobazam, in patients 2 years of age and older and for adjunctive treatment of seizures associated with TSC in patient 2 years of age and older. The most commonly reported side effects include somnolence; decreased appetite; diarrhea; transaminase elevations; fatigue, malaise, and asthenia; rash; insomnia, sleep disorder, and poor-quality sleep; infections; pyrexia; and vomiting. Serious side effects include hepatocellular injury, somnolence and sedation, suicidal behavior and ideation, hypersensitivity reactions, and withdrawal of ASMs. Further information is included in the latest GWP42003-P (Epidiolex) United States Prescribing Information and/or Summary of Product Characteristics.

Overall, based on the extensive clinical safety and efficacy results of GWP42003-P demonstrated across 5 Phase 3 studies, 2 open-label studies, and the EAP in the treatment of pediatric epilepsy syndromes, it is believed that GWP42003-P has a favorable benefit-risk profile for the treatment of EMAS.

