## 5. STUDY POPULATION

Investigators are responsible for confirming participant eligibility and will be required to maintain a log that includes limited information about all screened participants (initials, date of birth, and sex [as allowed per local regulations]) and outcome of screening.

Prospective approval of protocol deviations or waivers related to recruitment and eligibility criteria are not permitted.

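### Exclusion 50 re-applies every exclusion at Part B entry without exception, and exclusion 41 is literally met by everyone randomized in Part A

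*Combined protocol and SAP*

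**What the plan says.** Section 5.2 of the protocol opens with a rule under which one criterion is enough: "Participants are excluded from the study if ANY of the following criteria apply". Two exclusions are then reserved for Part B. Number 49 restates the liver-function rule for Part A Visit 9. Number 50 is general: "Meets any exclusion criteria at Part B Visit 1".

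Among the general exclusions, under the heading on clinical study experience, number 41 reads "Has previously been randomized, completed, or withdrawn from this study".

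On the inclusion side, Section 5.1 sets number 13 for Part B: "Has completed Part A of this study". Section 4.1 plans for rollover on the day of Part A Visit 9. The notes to Table 2 make that visit and Part B Visit 1 the same visit. Table 1 schedules a check of the criteria at Part A Visit 9 and says that Part B eligibility is confirmed there.

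On exceptions, Section 5 states: "Prospective approval of protocol deviations or waivers related to recruitment and eligibility criteria are not permitted".

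**The concern.** Exclusion 50 points back to a list written for entry into Part A. Most items on that list still make sense at rollover, such as pregnancy (27) or suicidality (45). Number 41 does not, because having been randomized in this study is a precondition for being considered for Part B at all. The text gives a site no way to tell which items carry over and which lapse.

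Part B's primary objective is long-term safety (Section 3.2), so its entry rule decides who contributes to that assessment. If the rule cannot be met as written, each site has to choose which exclusions still count. Choices may differ between sites, and an auditor comparing a rollover record with the protocol would find an exclusion that is met.

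**Working it through.** The plan states no figure on this point, so the check is logical. The relevant provisions are applied in order to one Part B candidate.

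1. **Inclusion 13 (Section 5.1).** The candidate has completed Part A of this study. The criterion's own wording makes Part A a part of what the protocol calls this study.
2. **Design (Section 4.1).** Participants are randomized on Day 1 of Part A, so completing Part A implies having been randomized in this study.
3. **Exclusion 41 (Section 5.2).** Its three limbs are joined by *or*. The *randomized* limb is met by step 2. It has no time window and no restriction to first entry. By contrast, exclusion 40, directly above it, is tied to a window before Part A Visit 1 and so is not triggered by Part A itself.
4. **Exclusion 50 (Section 5.2).** Any exclusion met at Part B Visit 1 excludes. By step 3, one is met.
5. **Way out.** Section 5 bars prospective waivers of eligibility criteria. Section 4.1 also mentions participants for whom the investigator judges continued treatment favorable, but nothing there sets Section 5.2 aside. Section 6.5 keeps the Part B eligibility criteria as a condition of the offer.

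In numbers: let N be the participants who complete Part A and wish to continue, with N at most 120 (Section 4.4). Those meeting exclusion 41 number N, which is 100%. Those who satisfy the entry rule as written number N − N = 0, whatever N is.

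Exclusion 49 bears on whether a reader should supply an unwritten exception. There the liver rule of exclusion 25 was rewritten for Part A Visit 9, so the drafters did adapt a criterion to Part B where they saw the need. Nothing similar was done for exclusion 41.

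**The case against.** The strongest reply is that exclusion 41 is a bar on re-enrolment. It sits among criteria about other or earlier trial participation. Section 4.1 describes one study in two parts, and Section 4.5 counts the entire study as complete only when both parts are. A participant at Part A Visit 9 is therefore continuing, and has neither completed nor withdrawn from the whole study. On top of that, inclusion 13 is specific to Part B and would ordinarily prevail over a general entry rule. Sections 4.1 and 6.5 describe the rollover, and Table 5 sets out a cross-titration for participants from both arms.

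Most of this stands as evidence of intent. It disposes of the *completed* and *withdrawn* limbs. It does not dispose of *randomized*, which describes every candidate, and no sentence says that inclusion 13 overrides exclusion 50.

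A reader might also infer that exclusions 31 and 43 bar the active arm (up to 60 participants). Section 2.3 says "GWP42003-P is purified CBD, approved in the US as Epidiolex", rollover skips the taper, and number 43 begins "Is currently using or has used recreational or medicinal cannabis, cannabinoid-based medications". The documents do not support this reading:

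- Section 6.8 restates both criteria among restrictions on concomitant therapy that run before screening and through the study. If they covered study drug, they would forbid it from Day 1 of Part A.
- Number 31 uses the commercial names under a heading on prior therapy, whereas the sections on study intervention speak of IMP or GWP42003-P.
- The only time point either criterion names is Part A Visit 1. It can be read as attaching to past use alone, but that is not the only reading.
- Part A treatment is still blinded at this visit (Section 6.3.2), so a criterion that turned on treatment arm could not be applied.

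Their application to IMP is ambiguous at most.

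**Conclusion.** The contradiction between exclusion 50, exclusion 41 and inclusion 13 is real and follows from the current text alone. As written, no rollover satisfies the entry rule: 0 of up to 120. The actual number of candidates will depend on the final sample size and on how many complete Part A. The conclusion assumes only that *randomized* in exclusion 41 has its ordinary meaning and that exclusion 50 means any exclusion, as it says.

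A reader might go further and infer that Part B would enrol nobody and that its safety objective could not be answered. The documents do not support that, because the intent to roll over Part A completers is plain throughout, and in practice Part B would probably enrol. Nor do they say that each rollover would be recorded as a deviation.

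What remains is an operative rule that gives the wrong answer if followed, inconsistent re-checking and audit exposure. Part A randomization, endpoints, estimands and analyses are untouched, and the Part B key secondary endpoints are descriptive (Section 9.4.3.1). It is a wording defect that should be corrected.

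**What to change.** Reword exclusion 50 so that it lists by number the exclusions re-checked at Part B Visit 1, and state that exclusion 41 does not apply to randomization in Part A of this study. That reconciles it with inclusion 13 and the planned rollover.

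For clarity only, add that study IMP does not count as a product covered by exclusions 31 and 43, in keeping with Section 6.8.

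The cost is a line or two in the next protocol amendment, with the site eligibility checklist for Part A Visit 9 brought into line. No dose, visit, endpoint or analysis changes.

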### **5.3. Lifestyle Considerations**

Note: Restrictions that apply to the period before the first admission are described in [Section 5.1](#) and [Section 5.2](#).

#### **5.3.1. Meals and Dietary Restrictions**

The caregiver will record the date, time, and meal type (eg, high-fat meal [dairy or meat], standard meal [fruit or vegetable], or other [if not fitting into one of the categories above]) for all meals consumed by the participant within 24 hours prior to PK collection.

### **5.4. Screen Failures**

Screen failures are defined as participants who consent/assent to participate in the clinical study but are not subsequently randomly assigned to the IMP. Documentation of screening failures will be collected and recorded in the eCRF. A minimal set of screen failure information is required to ensure transparent reporting of screen failure participants to meet the Consolidated Standards of Reporting Trials publishing requirements and to respond to queries from regulatory authorities. Minimal information includes demography, screen failure details, eligibility criteria, AEs, and any SAE.

#### **5.4.1. Rescreening**

Participants who do not meet the criteria for participation in this study (screen failure), or who could not be randomized within the screening/baseline window for logistical reasons, may be rescreened once at the discretion of the investigator or designee and after consultation with the medical monitor and/or sponsor representative. Rescreened participants must first be registered as screen failures in the eCRF and subsequently registered as rescreens in the eCRF. Once the participant is registered as rescreened, a new screening window will begin. For all rescreens, all screening procedures, including ICF, must be repeated. Sites should discuss planned rescreens with the medical monitor prior to rescreening (Part A Visit 1).

## 6. STUDY INTERVENTION(S) AND CONCOMITANT THERAPY

Study intervention is defined as any IMP or placebo intended to be administered to a study participant according to the study protocol.

### 6.1. Study Intervention(s) Administered

**Table 3: Study Interventions**

ARM Name	GWP42003-P	Placebo
Intervention Name	GWP42003-P	Placebo
Type	Drug	Drug
Dose Formulation	CBD dissolved in the excipients sesame oil and anhydrous ethanol (10% v/v), with sweetener (sucralose), and strawberry flavoring	The excipients sesame oil and anhydrous ethanol (10% v/v), with sweetener (sucralose), strawberry flavoring, and beta carotene
Unit Dose Strength(s)	100 mg/mL CBD	n/a
Dosage Level(s)	5 mg/kg/day (2.5 mg/kg BID) up to a maximum of 20 mg/kg/day	0.05 mL/kg/day up to a maximum of 0.2 mL/kg/day
Route of Administration	Oral	Oral
Use	Experimental	Placebo comparator
IMP or non-IMP	IMP	IMP
Sourcing	Provided centrally by the sponsor	Provided centrally by the sponsor
Packaging and Labeling	IMP will be provided in bottles with syringes for administration. Each bottle will be labeled as required per country requirement.	IMP will be provided in bottles with syringes for administration. Each bottle will be labeled as required per country requirement.
Current/Former Names or Alias	Cannabidiol	n/a

Abbreviations: BID = twice daily; CBD = cannabidiol; IMP = investigational medicinal product; n/a = not applicable; OS = oral solution.

### 6.2. Preparation/Handling/Storage/Accountability

The investigator or designee must confirm appropriate temperature conditions have been maintained during transit for all IMP received and any discrepancies are reported and resolved before use of the IMP.

Only participants randomized to receive IMP in the study may receive IMP and only authorized site staff may supply or administer IMP. All IMP must be stored in a secure, environmentally

controlled, and monitored (manual or automated) area in accordance with the labeled storage conditions with access limited to the investigator and authorized site staff.

For self-administration of IMP, participants/caregivers will be provided with bottle(s) containing the oral dosing solution along with oral syringes. Participants/caregivers will be trained, during Visit 3 at the study site, to self-administer IMP orally or with gastrostomy or nasogastric tubes BID (eg, morning and evening) preferably about the same time each day, consistently with or without food. Participants/caregivers will be provided with clear instructions for the dose escalation and taper dosing periods of the study via a printed dosing schedule and will record usage of IMP as part of the IMP dosing eDiary to aid in compliance.

Where required by local regulations, IMP may be dispensed more frequently than outlined in the schedule of assessments by completion of an unscheduled dispensing visit.

The investigator, institution, or the head of the medical institution (where applicable) is responsible for IMP accountability, reconciliation, and record maintenance (ie, receipt, reconciliation, and final disposition records).

Further guidance and information for the final disposition of unused IMP are provided in the pharmacy manual or other specified location.

## **6.3. Measures to Minimize Bias: Randomization and Blinding**

### **6.3.1. Randomization**

All participants will be centrally assigned to randomized IMP using an IRT (RTSM). Before the study is initiated, the log-in information and directions for the IRT will be provided to each site. Refer to [Section 8.1.3](#) for details on the IRT.

Training will be given to all sites prior to the start of the study.

The IMP will be dispensed at the study visits summarized in the SoA ([Section 1.3](#)).

Returned IMP should not be re-dispensed to the participants.

### **6.3.2. Blinding**

At the start of Part A, participants will be randomly assigned in a 1:1 ratio to receive GWP42003-P or matching placebo. Investigators will remain blinded to each participant's assigned IMP throughout the course of the study.

Participants entering Part B of the study, will first complete a 2-week blinded titration phase. Following the blinded titration phase, participants will start open-label treatment with GWP42003-P.

